## 7.3 Missing Data

### 7.3.1 OSCi

#### 7.3.1.1 General Imputation Rules

For analyses using the OSCi, including the primary and key secondary endpoints, subjects with an OSCi score of 8, indicating death, will have any subsequent missing OSCi assessments set as 8. In addition, if other data sources such as AEs indicate a patient has died all missing OSCi scores on and after the date of death will be set as 8. Any missing baseline OSCi scores will be imputed as 4, as per the study inclusion criteria.

#### 7.3.1.2 Imputation Rules for Time to Event Derived Endpoints

Primary analyses of time to hospital discharge and time to recovery will use a censoring approach for missing OSCi data for patients who discontinue the study prior to hospital discharge or recovery. I.e. patients who discontinue the study prior to hospital discharge or recovery and prior to day 28 will be censored at the date of their last OSCi assessment. However, this assumption of independent censoring will be tested in sensitivity analyses by multiple imputation of the time to hospital discharge and time to recovery. Further details are given in [Section 9.1.1.3](#).

#### 7.3.1.3 Imputation Rules for Binary Endpoints

Key secondary analyses will use the available data. Therefore, for subjects who withdraw from the study prior to day 35 this assumes that any progression to severe disease, intubation or death can only occur prior to study withdrawal. This assumption will be tested by using multiple imputation methods to impute the missing data. Further details are given in [Section 9.2.1.3](#).

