8.5.5 Handling of Missing Data

For analyses using the WHO OSCI, including the primary and key secondary endpoints, patients with a WHO OSCI score of 8, indicating death, will have any subsequent missing WHO OSCI assessments imputed as 8. In addition, if other data sources such as AEs indicate a patient has died all missing WHO OSCI scores on and after the date of death will be imputed as 8.

For relevant analyses, missing WHO OSCI assessments for patients who withdraw from the study alive will be imputed using multiple imputation under a missing at random assumption. Selected analyses will be repeated using a missing not at random approach through an imputation model estimated from patients in the placebo group.

For the mixed models with repeated measures (MMRM) of breathlessness, missing breathlessness scores will be imputed as 4 if the WHO OSCI score at the corresponding visit is ≥ 5 . Cough and sputum scores at corresponding visits will be considered missing at random and total BCSS scores will be calculated by summing the imputed symptom scores, where possible. Missing breathlessness, cough and sputum scores at all other visits will be considered missing at random and will not explicitly be imputed but will be accounted for by the MMRM analysis. Missing not at random approaches may also be considered for sensitivity analyses.

Further details regarding missing data approaches will be given in the SAP.

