### 5.3.1.3 *Progression to Severe Disease or Death within 35 days of First Dose or Randomisation*

Severe disease is defined by the OSCi as a score between 5 and 7. Death is defined by an OSCi score of 8. Any patient with an OSCi score at any post baseline assessment up to and including Day 35 of 5 or more will be considered as progressed to severe disease or death.

All patients should have an OSCi score of 4 at baseline, however in the event a patient is randomised with an OSCi score of  $\geq 5$  at baseline this patient will be excluded from all analyses of progression to severe disease or death.

Day 35 will be determined by the study schedule, which may be more than 35 days after randomisation if randomisation occurs before Day 1.

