## 7.6 Multiple Testing

A Hochberg procedure will be used to test the primary endpoints. Therefore, if the two-sided p-value for the estimate of time to hospital discharge is below 0.05 and the two-sided p-value for the estimate of time to recovery is below 0.05 the null hypotheses for both endpoints will be rejected. Otherwise, if the smallest of the two-sided p-values is below 0.025 only the null hypothesis associated with the smallest p-value will be rejected. In any other circumstance neither null hypothesis will be rejected.

The first key secondary endpoint will be formally tested using a two-sided alpha of 0.05 only if both primary endpoints are statistically significant. The second and third key secondary endpoints will be formally tested, in sequence, using a two-sided alpha of 0.05 only if all prior hypothesis tests are statistically significant.

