**9.2 Key Secondary Endpoints****9.2.1 Progression to Severe Disease or Death****9.2.1.1 Key Secondary Estimand**

The key secondary estimand will be the difference in probabilities for SNG001 versus placebo for progression to severe disease or death within 35 days of first dose of patients in the ITT population. Intercurrent events will be handled as per Table 14.

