**Table 14: Intercurrent events and policies for the key secondary estimand of progression to severe disease or death**

Intercurrent event	Policy
Death	Composite variable: The definition of the endpoint includes patients who die within 35 days of first dose, regardless of their OSCI assessments.
Premature treatment discontinuation and missed doses	Treatment policy: Severe disease will be determined regardless of treatment discontinuation and the number of missed doses.
Withdrawal from study	While-on-study: Patients will only be considered having severe disease if observed and recorded whilst participating in the study. This assumes the treatment effect is independent to reason for study withdrawal.
Other protocol deviations and concomitant medications affecting efficacy	Treatment policy: Severe disease will be determined regardless of any concomitant medication use or protocol deviations.

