**Table 20: Intercurrent events and policies for the key secondary estimand of death**

Intercurrent event	Policy
Premature treatment discontinuation and missed doses	Treatment policy: Death will be determined regardless of treatment discontinuation and the number of missed doses.
Withdrawal from study	While-on-study: Deaths which occur after study withdrawal will not be considered, unless consent is received to include death details in the clinical study database. This assumes the treatment effect is independent to reason for study withdrawal.
Other protocol deviations and concomitant medications affecting efficacy	Treatment policy: Death will be determined regardless of any concomitant medication use or protocol deviations.

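### The formally tested key secondary analyses score patients who withdraw event-free as Day 35 non-events, and the stated independence rationale does not support this

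*SAP*

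**What the plan says.** SAP 9.2.1.1 states its target, for all randomised patients, as follows: "difference in probabilities for SNG001 versus placebo for progression to severe disease or death within 35 days of first dose of patients in the ITT". SAP 9.2.2.1 and 9.2.3.1 define intubation or death, and death, in the same way.

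Under SAP 5.3.1.3 a patient has the first event if an observed post-baseline OSCI score up to Day 35 is high enough: a score "of 5 or more will be considered as progressed to severe disease or death". The intubation endpoint uses a threshold of 6. Death uses a score of 8 or a fatal adverse event by Day 35 (SAP 5.3.1.4 and 5.3.1.5).

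For withdrawn patients, SAP 7.3.1.3 says that "this assumes that any progression to severe disease, intubation or death can only occur prior to study withdrawal", and adds that multiple imputation will test this. Table 14 labels the strategy while-on-study and gives the reason: "This assumes the treatment effect is independent to reason for study withdrawal". Table 17 gives the same reason for intubation or death. Table 20 repeats it for death and adds: "Deaths which occur after study withdrawal will not be considered, unless consent is received to include death details in the clinical study database".

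The endpoints carry formal tests (SAP 7.6): "The first key secondary endpoint will be formally tested using a two-sided alpha of 0.05 only if both primary endpoints are statistically significant". Then: "The second and third key secondary endpoints will be formally tested, in sequence, using a two-sided alpha of 0.05", provided all earlier tests succeed.

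**The concern.** The ITT set keeps all randomised patients, and only observed events count. A patient still on oxygen who leaves the study on Day 4 therefore enters the logistic model as a Day 35 non-event. The quantity estimated is the probability of an event recorded before withdrawal. That depends on each arm's withdrawal rate as well as on its 35-day risk, which is the stated target.

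The rationale does not close this gap. Independence of withdrawal would support censoring, or imputation under missing at random; it gives no reason to set later risk to zero. For the primary endpoints SAP 7.3.1.2 does censor such patients.

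For death there is a further difficulty. Whether a death after withdrawal is counted can depend on whether someone learns of it and consent is obtained, so capture is incomplete and may depend on the outcome.

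At stake are three formally tested comparisons, one of them mortality, that can look better in the arm that loses more patients.

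**Working it through.** **Inputs from the documents.** 305 patients per arm. Dropout of 25% over 28 days, exponential (Protocol 8.1). The SAP 6 formula uses the same 28-day rate, but its text describes 25% as withdrawing before Day 35, so both readings are used.

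**Assumptions.** The documents give no event rate, effect or timing for any key secondary endpoint. The true risks and timings below are assumed. Withdrawal is taken as fully independent of outcome, which is at least as favourable as the stated rationale.

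**Step 1: the planned withdrawal.** Rate d = ln(100/75)/28 = 0.01027 per day, which reproduces 25% at Day 28. If it continues to Day 35, 1 - exp(-35d) = 30.2%, or 92 patients per arm before removing those with an earlier event. At 25% by Day 35 the number is 0.25 x 305 = 76 per arm.

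**Step 2: risk that the rule records, for a true 35-day risk p.**
- Constant hazard: with h = -ln(1 - p)/35, recorded risk = h/(h + d) x [1 - exp(-35(h + d))].
- Early events (truncated exponential, k = 1/mean parameter): p x k/(k + d) x [1 - exp(-35(k + d))]/[1 - exp(-35k)].
- Evenly spread events: p x [1 - exp(-35d)]/(35d).

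Example: p = 15% v 10%, constant hazard, 25% by Day 28. For p = 15%, h = 0.00464, and the recorded risk is 0.311 x 0.407 = 12.7%. For p = 10% it is 8.4%. The difference is -4.2 points instead of -5.0.

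**Step 3: fraction of the risk difference retained, equal withdrawal in both arms.**

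| Event timing | 25% by Day 28 | 25% by Day 35 |
|---|---|---|
| Early, mean parameter 4 days | 0.961 | 0.968 |
| Early, mean parameter 7 days | 0.935 | 0.947 |
| Constant hazard, 15% v 10% | 0.847 | 0.875 |
| Constant hazard, 6% v 3% | 0.842 | 0.871 |

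The loss is about 4-16% on the first reading and 3-13% on the second. Evenly spread events give 0.302/0.360 = 0.840 on the first.

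**Step 4: effect on the test, equal withdrawal.** For 15% v 10%, the true odds ratio is (0.10/0.90)/(0.15/0.85) = 0.63; the recorded one is at most 0.635. Approximate power at 305 per arm falls from 46% to 40-45%. For 6% v 3% it falls from 43% to 37-42%. With no true effect both recorded risks are equal, so there is no bias.

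**Step 5: unequal withdrawal, no true effect (illustration only).** Take a true risk of 10% in both arms and withdrawal of 15% v 35% per 28 days.
- Evenly spread events: captured fractions 0.905 and 0.773, so 9.05% v 7.73%, a spurious 1.3 points.
- Early events (mean parameter 5 days): 0.972 and 0.929, so 9.72% v 9.29%, a spurious 0.4 points.

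The standard error of the larger contrast is sqrt[(0.0905 x 0.9095 + 0.0773 x 0.9227)/305] = 2.2 points, so 1.3 points is about 0.6 standard errors.

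**Step 6: general form.** True difference = recorded difference + w(active) x r(active) - w(placebo) x r(placebo), where w is the fraction withdrawn event-free and r their unobserved event risk. With w = 25% in both arms, a 10-point gap in r moves the result by 2.5 points.

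**The case against.** **The rule is disclosed and will be tested.** SAP 9.2.1.3 plans a tipping-point analysis by arm in which delta = 1 is missing at random, a jump-to-reference imputation and a completers analysis. SAP 9.2.2.3 and 9.2.3.3 extend the missing-data analyses to the other two endpoints. This stands, and it limits the point to which analysis is formal.

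**A reader might infer that the SAP demoted a Protocol rule.** Protocol 8.5.5 says that "missing WHO OSCI assessments for patients who withdraw from the study alive will be imputed using multiple imputation under a missing at random assumption". But that sentence is confined to relevant analyses. The Protocol's own key secondary estimand is while-on-study, and Protocol 8.4.2 lists imputation for withdrawn patients as sensitivity work. The SAP follows the Protocol here.

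**A reader might infer that every withdrawn patient is scored alive.** The documents do not go so far. A fatal adverse event by Day 35 counts (SAP 5.3.1.5). Death shown by another data source sets later missing scores to 8 (SAP 7.3.1.1). Consented later deaths count (Table 20). Protocol 5.5 also separates stopping medication from leaving the study and continues contact attempts to Day 90.

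**The effect is modest.** The p-value in SAP 9.2.1.2 is listed with the odds ratio, which hardly moves under balanced withdrawal. The 15% v 35% contrast has no source in the documents. Many leavers may already be discharged and at low risk: the planning model has 70% of placebo patients discharged by Day 28. All of this stands.

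**The remedy is not only wording.** SAP 9.2.1.3 itself says that imputation moves withdrawal to a treatment policy. It also recognises that the day-by-day model can become over-parameterised, and Protocol 8.5.2 foresees too few events for the second and third endpoints. This stands as a cost.

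None of it answers the core point: independence does not make no later event the right value for a withdrawn patient.

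**Conclusion.** The point holds in a limited form. The formally tested analyses target a 35-day ITT probability but treat later risk after event-free withdrawal as zero, apart from deaths that become known, and the rationale in Tables 14, 17 and 20 does not support that.

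At the planned 25% withdrawal, independent and balanced, the risk difference is too small by about 3-16% across the two readings of that figure and the event timings tried. The odds ratio and the null are then essentially unaffected, and power falls by about 1 to 7 percentage points in the cases tried. It would be wrong to conclude that the tests are invalid whenever patients withdraw. Bias under the null needs unequal withdrawal. Even a wide illustrative imbalance gives a spurious 0.4 to 1.3 points at a true 10% risk, and less if leavers are mostly discharged patients.

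Risks, timings and the imbalance are assumptions. What does not depend on them is the direction: other things equal, losing more patients improves an arm's recorded result. This should be changed, but it does not by itself undermine the trial.

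**What to change.** 1. Make the delta = 1 imputation in SAP 9.2.1.3 (logistic imputation on treatment, covariates and the previous two days' OSCI scores, combined by Rubin's rules) the formal analysis for all three key secondary endpoints. Keep the current withdrawn-as-non-event analysis as a sensitivity analysis.
2. Align the withdrawal rows and their rationale in SAP Tables 14, 17 and 20, Protocol 8.4.2 and the Protocol synopsis, and record the change in SAP Section 15.
3. In Protocol 5.5, which already asks sites to try to document outcome, have sites ask each withdrawing patient for permission to record vital status at Day 35.

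Cost: amended wording in both documents, an open change of the withdrawal strategy from while-on-study to treatment policy, slightly wider intervals, and reliance on a day-by-day model that may be unstable when intubations or deaths are few. No new analysis method is needed.

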### 7.3.2 BCSS

Missing breathlessness scores will be imputed according to the OSCi score at the corresponding date of assessment. If the OSCi score  $\geq 5$  at the same assessment as the missing breathlessness score then the breathlessness score will be imputed as 4 (the maximum breathlessness). At all other assessments breathlessness will be assumed Missing at Random (MAR). Missing cough and sputum scores will be assumed MAR at all days. MAR assessments will not be explicitly imputed but will be assessed as such by the analysis method. For the calculation of total BCSS score at days where breathlessness has been imputed as 4, the cough and sputum scores from the last observed days will not be imputed if missing and therefore the total BCSS score will be missing at these days.

### 7.3.3 Partial Dates

For adverse events, partial dates will only be imputed for the purposes of determining treatment emergence. The following rules will be applied:

- If only the AE start day is missing and the AE start month is on or after the month of first dose then the AE will be considered treatment emergent.
- If the AE start day and month are missing and the AE start year is on or after the year of first dose, then the AE will be considered treatment emergent.

- If the AE start date is completely missing, then the AE will be considered treatment emergent.

Due to the requirement that dosing is started within 24 hours of consent AE end dates will not be taken into consideration.

For medications, partial end dates will be imputed only to determine medication categorisation as prior or concomitant. If the end date is missing the medication will be assumed concomitant. Otherwise, partial end dates will be imputed as the latest possible date (last day of the month if the day is missing or 31st December if the day and month are missing). If the imputed date is after the first dose date the medication will be assumed concomitant.

## 7.4 Interim Analyses and Data Monitoring

### 7.4.1 Purpose of Interim Analyses

Two types of interim analysis will be used during the trial:

- DSMC meetings for the purpose of ongoing review of safety data.
- An interim analysis of unblinded efficacy data to allow for early stopping of the trial due to futility will be conducted if it is feasible for the interim data to be analysed and interpreted within a timeframe which is ethical and of scientific value to the study.

In addition, a primary analysis will be conducted once all patients have completed their day 35 assessment or have withdrawn from the study (i.e. once all data required for the evaluation of the primary and secondary endpoints has been entered into the clinical study database and that data has been locked). This analysis will be conducted by the main statistical team, who will be fully unblinded at the point of database lock.

### 7.4.2 Planned Schedule of Interim Analyses

The first DSMC meeting will occur prior to the 100th patient completing study treatment. Further DSMC meetings will be organised as required or as requested by the DSMC. For further details refer to the DSMC charter.

The interim analysis for futility will occur after the first 300 randomised patients have completed day 35 or have withdrawn from the study if it is feasible for the interim data to be analysed and interpreted within a timeframe which is ethical and of scientific value to the study.

### 7.4.3 Scope of Adaptations

As per the DSMC charter the DSMC may provide recommendations about necessary changes to the study protocol and also whether to stop or continue the study.

Regarding the interim analysis for futility, non-binding futility rules will be documented in the Independent Data Monitoring Committee (IDMC) charter. Following the futility analysis, the IDMC will meet to review the unblinded data and will make a recommendation to either continue the study or to stop the study due to futility. The IDMC may also recommend stopping the study due to safety concerns or due to evidence of

a paradoxical treatment effect between recovery/discharge and disease progression or death regardless of success versus the futility criteria. No sample size adjustments are planned.

#### **7.4.4 Adjustment of Confidence Intervals and p-values**

The interim analysis will be used to assess futility only. The trial will not be stopped due to efficacy. Therefore, no alpha adjustment is required for the inclusion of the interim analysis and the global alpha of 0.05 will be preserved for the final analysis.

#### **7.4.5 Practical Measures to Minimise Bias**

As per the DSMC charter version 2, unblinded outputs will be provided from the second DSMC meeting onwards. An independent statistical team will generate unblinded outputs and those results will be shared with unblinded team members only. In addition, an independent statistician who will have no input to the study conduct post unblinding will attend the DSMC closed sessions. The unblinded statistical team will have no input to the study conduct post unblinding and will not be involved in the programming or generation of blinded outputs post unblinding.

The interim analysis for futility will be produced by an independent statistical team who will have no input to the study conduct post unblinding and will not be involved in the programming or generation of blinded outputs post unblinding. Unblinded results will be shared with unblinded team members only. The recommendation to continue or stop the study will be guided by pre-defined criteria documented in the DSMC charter.

The main statistical team will be fully unblinded at the point of the primary analysis database lock. However, it is expected this will occur prior to the completion of all follow-up assessments. Therefore, to ensure these uncompleted assessments are not biased by knowledge of the randomised treatment to individual subjects, unblinded outputs will be released to the unblinded team at an aggregate level only. Individual randomisation assignments may be released to study team members who will have no further input into the study conduct, where required for decision making. Any changes to the planned analysis following unblinding for the primary analysis will be documented as such in the Clinical Study Report (CSR).

Full details will be documented in an unblinding plan.

#### **7.4.6 Documentation of Interim Analyses**

A snapshot of the data, programs, Study Data Tabulation Model (SDTM) and ADaM datasets and outputs for DSMC and IDMC meetings and the primary analysis will be archived at the point of delivery and included in the blinded/unblinded study master file (SMF) and trial master file (TMF), as appropriate.

### **7.5 Multi-centre Studies**

This study will be conducted by multiple investigators at multiple centres internationally. Randomisation to treatment arms is stratified by centre. When specified, statistical analysis will be adjusted for geographic region. Geographic region will be categorised as per table 4. If not many patients are recruited in the sites of the Latin American region resulting in analytical issues such as non-convergence, Latin

America patients may be combined with those of India for some or all planned covariate adjusted analyses.

**Table 4: Geographic regions for the purpose of analysis**

Geographic Region	Country
Latin America	Argentina, Brazil, Colombia, Mexico
Europe and USA	Belgium, France, Germany, Israel, Italy, Netherlands, Portugal, Romania, Serbia, Spain, United Kingdom, United States of America
India	India

